### 6.2.2 Sample

In Florida, only 4.3 percent of children ages 11 to 17 are current cigarette smokers. However, e-cigarette use is increasing from 5 percent of Florida high school students in 2013 to 11 percent in 2014. While the percentage of adolescents at risk to begin smoking is not known, studies have identified maternal smoking, trying tobacco, alcohol or marijuana by 8th grade, and endorsement of sensation seeking behavior as risk factors for tobacco and related product use. Children should be screened for these risks.

We will screen all youth, ages 11 through 17 years, in the practice for current tobacco use and risk behaviors associated with cigarette and nicotine product use with the goal of reaching 20 children per practice who are current tobacco users who could receive at least one or more of Steps 3 through 6 (advise, assess, assist, arrange). To achieve 20 patients per practice who reach the “advise” and “assess” stages, if the practice had the average percentage of children using e-cigarettes, approximately 218 patients would need to be screened. The number screened to reach the “advise” and “assess” stages is based on the e-cigarette use and not the traditional cigarette use.

Intervention practices will be asked to screen patients for tobacco and nicotine product use (using the anticipate and ask components of the 6As) by having youth complete a tobacco and nicotine use screening tool until the practice has identified and completed at least the “advise” and “assess” intervention on 20 tobacco/nicotine users. Parental consent and adolescent assent will be electronically obtained using ResearchActs software. In addition, practices will be asked to implement a short parental screening tool for tobacco use. The parent and child will respond to the surveys separately. After the child completes the survey s/he will be offered a \$5 electronic Amazon gift card.

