Congruence between documentation of the intervention in the EHR and adolescent report of the intervention: Within 30 days post primary care visit, patients will be contacted via telephone to complete the Tobacco and Nicotine Product Primary Care Questionnaire (TNP-PCQ) (Appendix E), which asks about their recollection of the tobacco and nicotine product discussions with their providers during the primary care visit. For each outcome in the TNP-PCQ survey, we will perform a concordance analysis to evaluate the agreement between the medical record review data and patient-reported data. Concordance will be evaluated using the following statistics: sensitivity, specificity, positive predictive value (PPV), negative predictive value (NPV) and the Kappa statistic. Differences in concordance will be tested with the Pearson chi-square test.

**7. Possible Discomforts and Risks.** There are no known risks associated with this study. The only discomfort that the patient may experience may be associated with discussing something that is personal. Patients will be reminded that they can skip any question on the survey questionnaire that they wish. Patients will be informed that they can choose not to participate in in any portion of the discussion and that answering questions is completely voluntary. There is minimal risk in working with personal health information. However, all data will be in a secure database with access limited to a programmer and the study members conducting data analysis. The medical records will be reviewed onsite and will not leave the practice setting or will be reviewed through a secure computer access if permission is granted for UF Health sites.

**8. Possible Benefits.** There are no potential benefits to patient participation.

**9. Conflict of Interest.** None.

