**Best Practice:**

1. Documentation that youth was asked about current use of:
  - a. Cigarettes
  - b. Cigars/Cigarillos
  - c. E-cigarettes
  - d. Hookah
  - e. Smokeless tobacco products
2. If youth smokes or uses nicotine products, was youth asked about amount used (e.g., just a puff, 5 cigarettes a day and so on)?
3. If youth smokes or uses nicotine products, was youth asked about how often used (e.g., daily, monthly and so on)?
4. Was youth asked if he/she anticipated using cigarettes or nicotine products in the future?
5. Was youth advised to not use: Cigarettes, Cigars/cigarillos, E-cigarettes, Hookah, or Smokeless tobacco products
6. For those who smoke or use tobacco products was youth asked if they were ready to quit?
7. For those who were ready to quit, was a referral made?
8. Regardless of readiness to quit, were youth given or told about resources that are available to learn more about the hazards of tobacco and nicotine use?
9. Regardless of readiness to quit, was youth given/told about resources to quit should s/he decide to do so?
10. Was parental tobacco use assessed?
11. Were parent(s) asked about?
  - a. Smoke free home
  - b. smoke free car
  - c. If anyone caring for the child smokes
12. If parent(s) smokes or uses nicotine products in the home or car, was s/he advised to quit smoking?
13. If parent(s) smokes, was s/he referred to smoking cessation programs?
14. If parent(s) smokes was s/he told about educational resources on the influence of parental smoking on the child/youth?

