### INTRO3

- All your answers are confidential. We will not report your name or individual responses to your pediatrician/healthcare provider.
- I do not work for your doctor's office. Your doctor's office is part of the OneFlorida Clinical Research Consortium. This is a group of clinics that work together to conduct research in clinical settings. I work for a Survey Research Center and I have been asked by the University of Florida to call study participants to ask about their opinions and experiences. If you have any questions about the study, please contact [name] at [contact]. If you have any questions about your health care, please contact your provider's office.

**1. During this last visit** that you had with a doctor or other health provider, did you complete a checklist or survey about your use of cigarettes and/or other nicotine products (for example e-cigarettes, hookah and snuff)?

- 1  Yes  
 2  No  
 12  Don't Know  
 13  Refused

**2. During this last visit**, did you get a chance to speak with a doctor or other health provider privately? (Meaning one on one - without your parents or other people in the room).

- 1  Yes  
 2  No  
 12  Don't Know  
 13  Refused

**3. During this last visit**, did a doctor or other health provider tell you that what you talked about with them was confidential? (Meaning it would not be shared with anyone else).

- 1  Yes  
 2  No  
 12  Don't Know  
 13  Refused

**4. During this last visit**, did a doctor or other health provider talk with you about any of the following?

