**D. Smoking hookah?**

- 1  Yes →.  
 2  No →  
 12  Don't Know →  
 13  Refused →

5. How helpful was this discussion in understanding the risks of cigarettes or using any nicotine products such as e-cigarettes to your health?

- 1  Not at all helpful  
 2  Somewhat helpful  
 3  Helpful  
 4  Very helpful  
 5  Not sure  
 13  Refused

6. **During this last visit**, did you and a doctor or other health provider talk about how and why to quit smoking or using nicotine products (such as setting a date to quit)?

- 1  No because I do not smoke or use nicotine products  
 2  Yes → **If YES go to 7.**  
 2  No → **If NO go to 8.**  
 3  No, because I did not tell my doctor or other health provider that I smoke cigarettes or use nicotine products → **If NO go to 8.**  
 12  Don't Know → **If DON'T KNOW go to 8.**  
 13  Refused → **If REFUSED go to 8.**

7. How helpful were your discussions in quitting smoking or using nicotine products?

- 1  Not at all helpful  
 2  Somewhat helpful  
 3  Helpful  
 4  Very helpful  
 5  Not sure

8. **During this last visit**, did a doctor or other health provider ask you if your parents or anyone else living with you smoked cigarettes or used nicotine products?

- 1  Yes. **Go to 9**  
 2  No. **Go to** closing thank you  
 12  Don't Know **Go to** closing thank you  
 13  Refused **Go to** closing thank you

9. **During this last visit**, did a doctor or other health provider talk to you a parent or family member about quitting smoking or using nicotine products?

- 1  No because no one living with me smokes cigarettes or uses tobacco products  
 2  Yes **Go to** closing thank you  
 3  No **Go to** closing thank you  
 4  No because my parent/family member did not tell the doctor (or health care provider) they smoke or use nicotine products **Go to** closing thank you  
 12  Don't Know **Go to** closing thank you  
 13  Refused **Go to** closing thank you

**Those are all of the questions we have. In order to receive your \$5.00 Amazon electronic gift card, we need to verify that we have your correct address and email address.**

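### Aim 3 promises agreement statistics for every telephone outcome, but the nearest chart items on quit advice and parental use record different events, so agreement can be poor with perfect charting and recall

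*Combined protocol and SAP*

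**What the plan says.** Section 6.2.5 (Analysis Plan, paragraph on congruence) sets the scope: "For each outcome in the TNP-PCQ survey, we will perform a concordance analysis to evaluate the agreement" between medical record data and patient report. It continues: "Concordance will be evaluated using the following statistics: sensitivity, specificity, positive predictive value (PPV), negative predictive value (NPV) and the Kappa statistic". Differences in concordance are then to be tested with a Pearson chi-square test. The section does not say which chart item goes with which telephone item, which youth enter each table, which source is the reference, or how qualified negatives, don't-know answers and refusals are scored.

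The telephone form is Appendix F (section 6.2.5 labels it Appendix E). Item 6 asks "did you and a doctor or other health provider talk about how and why to quit smoking or using nicotine products", with setting a quit date as its example, and its first response option is "No because I do not smoke or use nicotine products". Item 8 asks "did a doctor or other health provider ask you if your parents or anyone else living with you smoked cigarettes or used nicotine products". Other items have no chart counterpart, for example item 2: "did you get a chance to speak with a doctor or other health provider privately".

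The chart form is Appendix E. Its only item on advice to the youth, item 5, records advice not to use any of five product types and is not limited to users. Item 10 reads "Was parental tobacco use assessed" and names no informant. Item 11 concerns questions put to the parents.

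Section 6.2.2 says of the screening surveys: "The parent and child will respond to the surveys separately". Its paragraph on patient participation includes clinician screening and advising time for the child and for the parent, and this covers youth who do not use nicotine products.

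**The concern.** An agreement statistic can be read as documentation quality or recall quality only if both sources answer the same question about the same people. Here a correct chart and a correct memory can give opposite answers:

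- A non-user advised not to start is a yes on chart item 5 and a no on telephone item 6.
- A visit where the parent was asked and the youth was not is a yes on chart item 10 and a no on telephone item 8.

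A low kappa on these topics would probably be reported as poor charting or poor recall when it may be neither. The problem cannot be repaired after abstraction, because the chart form has no field for a documented quit discussion and none for the youth being asked about household use.

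**Working it through.** The documents give no expected kappa, agreement target or sample size for Aim 3, so there is no planned figure to reproduce. The check assumes no charting or recall error and asks what agreement the mismatch alone produces.

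**Items side by side**

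| Topic | Telephone (Appendix F) | Chart (Appendix E) | Match |
|---|---|---|---|
| Products | 4A–D: provider talked about chewing tobacco or snuff, cigarettes, e-cigarettes, hookah | 1e, 1a, 1c, 1d: youth asked about current use | Adequate |
| Quitting | 6: how and why to quit; non-users answer a form of no | 5: advised not to use, any youth | Different event and denominator |
| Parental use | 8: youth asked about parents or household | 10: parental use assessed, any informant | Different informant and scope |
| Parent quitting | 9: asked only after yes to 8 | 12: parent who uses in home or car advised to quit | Only within a restricted group |
| Checklist, privacy, confidentiality, helpfulness | 1, 2, 3, 5, 7 | None | Not computable |

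**Formulas.** With cell proportions A (both yes), B (chart yes, telephone no), C (chart no, telephone yes) and D (both no): po = A + D; pe = (A+B)(A+C) + (C+D)(B+D); kappa = (po − pe)/(1 − pe). Taking the telephone as reference, specificity = D/(B+D).

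**Quit pair, all youth.** User share u: section 6.2.2 implies 20/218 = 9.2% and also cites 11% e-cigarette use. Assumptions: every user is advised and has the quit discussion; a share a of non-users is advised not to use. The documents do not give a. Then A = u, B = (1−u)a, C = 0, D = (1−u)(1−a).

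For u = 0.0917 and a = 0.5: po = 0.0917 + 0.4541 = 0.546; pe = 0.5459 × 0.0917 + 0.4541 × 0.9083 = 0.4625; kappa = 0.0833/0.5375 = 0.155.

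| a | kappa, u = 9.2% | kappa, u = 11% |
|---|---|---|
| 0 | 1.00 | 1.00 |
| 0.10 | 0.62 | 0.66 |
| 0.50 | 0.16 | 0.18 |
| 0.90 | 0.02 | 0.02 |
| 1 | 0 | 0 |

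**Quit pair, users only.** The Background section reports that 81% of pediatricians advise patients who smoke to quit and one-third discuss cessation strategies. These are shares of pediatricians. Treat them, for illustration only, as patient rates with the second group inside the first. Then po = 0.333 + 0.19 = 0.523; pe = 0.81 × 0.333 + 0.19 × 0.667 = 0.397; kappa = 0.127/0.603 = 0.21. Restricting to users does not by itself match the events.

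**Parent pair.** Assume parents are assessed directly in a share p of visits and, independently, youth are asked in a share y. Chart item 10 is yes if either happened. Then A = y, B = (1−y)p, C = 0, D = (1−y)(1−p), so specificity = 1 − p. The documents give neither p nor y.

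| p | kappa for y from 0.1 to 0.9 | specificity |
|---|---|---|
| 0 | 1.00 | 1.00 |
| 0.10 | 0.64 to 0.94 | 0.90 |
| 0.50 | 0.17 to 0.64 | 0.50 |
| 0.90 | 0.02 to 0.17 | 0.10 |
| 1 | 0 | 0 |

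At p = 1 the chart answer is always yes, so raw agreement equals y and can reach 90% at y = 0.9 while kappa is 0.

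**The case against.** The strongest reply is that the plan names no pairs, so the poor tables come from a pairing it never adopted. The Background defines the Advise step as advice to quit, section 6.2.3 reviews each record through the steps applicable to that patient, and telephone item 6 lets an analyst set non-users aside. A sensible analyst would restrict to users. That answers the denominator but not the event: chart items 5, 6, 7 and 9 record advice not to use, readiness, referral and resources, and none records a quit discussion.

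It is also fair that a, p and y are not given and may be low, notably in usual care. Nor do the documents say that completing the parent questionnaire creates a chart entry. This rules out any claim that agreement is bound to be poor. But Aim 3 concerns documentation of the intervention, and the intervention as planned includes advising non-users and screening parents.

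Four stronger readings are tempting, and the documents do not support them:

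- That the primary adherence analysis is affected. Its outcomes come from medical records alone.
- That the unmatched telephone items yield wrong results. With no chart variable, no statistic can be computed.
- That the chi-square test is invalid because items come from the same youth. The comparison is unstated and could be between arms, since Figure 2 lists child-reported outcomes in both.
- That telephone item 6 cannot be scored because yes and no are both printed with code 2. The two answers route differently, and the code may be a conversion artefact.

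**Conclusion.** The concern holds in conditional form. For quit advice and parental use, the nearest chart and telephone items differ in event, informant or denominator, so Aim 3 cannot separate that difference from poor documentation or recall. Chance-corrected agreement can be near 0 without any error, and it falls as more non-users are advised and more parents are assessed directly. A reader might infer that poor agreement is certain. It is not: the sizes rest on assumed rates, kappa is moderate to high when those rates are low, and raw agreement on parental use can be high even when kappa is 0. The product items are not affected. One of three aims is at stake in a pilot with no decision threshold tied to it. The change should be made, but it does not threaten the primary outcome.

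**What to change.** Before record abstraction starts, replace the reference to each outcome in section 6.2.5 with a named list of pairs, giving event, informant and denominator for each:

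- Keep telephone 4A–D with chart items 1e, 1a, 1c and 1d.
- Pair telephone item 6, users only, with a new chart item in the same terms (quit discussion documented). An advised-to-quit item would not match.
- Pair telephone item 8 with a new chart item recording that the youth was asked about parental or household use, or drop item 8 from concordance.
- Use telephone item 9 against chart item 12 only among youth who answered yes to item 8 and whose parent smokes, or report it descriptively.
- Report telephone items 1, 2, 3, 5 and 7 descriptively.
- State how qualified negatives, don't-know answers and refusals are scored, and which source is the reference.
- Check that yes and no on telephone item 6 carry different codes.
- State what the chi-square test compares, and use it only for independent groups.

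The cost is a revised paragraph and one or two extra abstraction items. Fewer pairs will be reported, and the quit pair will rest on users only, so its estimate will be imprecise.

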## 5. Specific Aims:

**Aim 1:** Develop and deploy an electronic short screening tool for tobacco and nicotine product use into pediatric primary care workflow in conjunction with 1) clinician and office staff training on the 6As and parent screening through the use of trained Clinical Practice Facilitators (CPFs), 2) clinician-engaged adaptations of the intervention to fit their practice workflow, and 3) support for Maintenance of Certification (MOC) to engage pediatricians in implementing the best practices.

[figure not shown]
**Aim 2:** Gather pilot data about the effectiveness of the intervention on clinician adherence to best practices and changes in practice capacity for change, adaptive reserve, and clinician self-efficacy.

**Aim 3:** Examine the congruence between documentation of the intervention in the EHR and youth report of the intervention.

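### The telephone survey has no item for Anticipate or Assess and blends Advise with Assist, so Aim 3 covers less than the intervention it names

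*Combined protocol and SAP*

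**What the plan says.** Section 5 gives Aim 3 as: "Examine the congruence between documentation of the intervention in the EHR and youth report of the intervention". Section 4 defines the intervention step by step as the 6As, and Sections 3 and 5 add parent screening.

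Section 6.2.5 sets out the analysis: "For each outcome in the TNP-PCQ survey, we will perform a concordance analysis to evaluate the agreement" between record-review and youth data. The statistics are "sensitivity, specificity, positive predictive value (PPV), negative predictive value (NPV) and the Kappa statistic". No list of outcomes and no map from survey items to chart items is given. (That paragraph cites the survey as Appendix E; the survey is Appendix F, and Appendix E is the chart form.)

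Appendix E has Yes/No fields for most steps:

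- Ask: "Documentation that youth was asked about current use of", followed by five products.
- Anticipate: "Was youth asked if he/she anticipated using cigarettes or nicotine products in the future".
- Advise: "Was youth advised to not use: Cigarettes, Cigars/cigarillos, E-cigarettes, Hookah, or Smokeless tobacco products".
- Assess: "For those who smoke or use tobacco products was youth asked if they were ready to quit".
- Assist: referral and resources, items 7 to 9.

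Appendix F asks about completing a checklist (Q1), privacy (Q2), confidentiality (Q3), talk about four product types (Q4A to Q4D), helpfulness (Q5, Q7), household use (Q8) and talk about a family member quitting (Q9). Its one question on the youth's own quitting, Q6, asks whether youth and provider did "talk about how and why to quit smoking or using nicotine products (such as setting a date to quit".

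**The concern.** Agreement can be examined only for a step that both sources record. The chart form records whether future use and readiness to quit were raised, but the survey never asks the youth about either. Assess matters most here: Section 6.2.2 counts a user towards the goal of 20 per practice only once both Advise and Assess have been completed. The trial would therefore hold chart documentation of a step that every counted user must receive, with no youth report to set against it.

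The plan also promises a concordance analysis for each survey outcome, yet several survey items ask about things the chart form does not record. Without a list of pairs, the analyst must decide what to compare with what, possibly after seeing the data. A question left off the call cannot be recovered later.

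**Working it through.** The documents give no figure for Aim 3 to reproduce, so the check is an item map. Inputs are the step definitions in Section 4, the chart fields in Appendix E and the questions in Appendix F.

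**1. Step by step**

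| Step | Appendix E (chart) | Appendix F (survey) |
|---|---|---|
| Anticipate | item 4 | none |
| Ask | items 1a–1e, 2, 3 | Q4A–Q4D, matching 1e, 1a, 1c, 1d; none for cigars (1b), amount (2) or frequency (3) |
| Advise | item 5 | Q6, shared with Assist |
| Assess | item 6 | none |
| Assist | items 7, 8, 9 | Q6, shared with Advise; nothing specific to referral or resources |
| Arrange | none | none |
| Parent component | items 10–14 | Q8 (item 10, loosely 11c); Q9 (item 12) |

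No survey item: 3 of 6 steps. Sharing one item: 2 of 6. Own items: 1 of 6. (3 + 2 + 1 = 6.)

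**2. Survey to chart.** Q1–Q3 (3), Q4A–Q4D (4) and Q5–Q9 (5) make 3 + 4 + 5 = 12 items. Q1, Q2, Q3, Q5 and Q7 have no chart field: 5 of 12. Each planned statistic needs a chart Yes/No paired with a youth Yes/No, so none can be computed for these five. Q6 also lacks a clean match, because Appendix E has no quit-date field and none for how and why to quit. Five is therefore the lower count, and six is defensible.

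**3. Chart to survey.** Appendix E has 5 (1a–1e) + 9 (2–10) + 3 (11a–11c) + 3 (12–14) = 20 elements.

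- Generous map (Q6 credited to items 5, 7 and 9; Q8 to 10 and 11c): 4 + 3 + 2 + 1 = 10 covered, 10 not.
- Strict map (Q6 credited to none; Q8 to item 10 only): 4 + 0 + 1 + 1 = 6 covered, 14 not.
- Youth-directed elements only (1a–1e and 2–9, 5 + 8 = 13): 7 covered on the generous map, 4 on the strict one.

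Anticipate (item 4) and Assess (item 6) are uncovered on both maps.

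**4. What Q6 can carry.** A Yes may mean advice to quit, talk about how to quit, or a quit date, so it cannot be assigned to Advise or to Assist. For non-users it carries less still. Section 6.2.2 expects 20 users among about 218 screened: 20/218 = 9.2%, leaving 90.8% non-users. With the 190 per practice in Section 6.2.3, 20/190 = 10.5%, leaving 89.5%. Q6 offers non-users a reply that no quit talk took place because they do not use these products. Chart items 4 and 5 are not restricted to users. For about nine in ten expected respondents, youth report of counselling thus rests on Q4, Q8 and Q9, with no distinct item on future use or on advice not to use.

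**5. Against the primary measures.** Section 6.2.5 names three: talk about the patient's own use (Q4), quit advice (Q6, blended) and talk about parental use (Q8). Each has a survey item.

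**The case against.** A reader might infer that Aim 3 cannot examine most of the intervention. The documents do not support that. Three of six steps lack any survey item, which is half; five of six follows only if Q6 is rejected for both Advise and Assist. The 6As are also not the whole intervention: parent screening belongs to it and is reached by Q8 and Q9. All three named primary measures have some youth report.

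A reader might also blame the survey for Arrange, or conclude that 5 of 12 planned analyses fail. Arrange is missing from the chart form too, so a survey item alone would give no pair. Section 4 defines it partly as contact after the quit date, which may fall later than a call made about 30 days after the visit. As to the five items, Section 6.2.5 speaks of outcomes, not items, and helpfulness ratings are unlikely targets for kappa. Figure 2 lists child-reported visit outcomes in their own right, so unpaired items still have a use. This part is an ambiguity to settle, not an analysis that must fail.

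Finally, this is a pilot, Aim 3 carries no hypothesis, and the primary outcome comes from medical records. The gain for user-only items is modest: at the goal of 20 per practice, 2 × 20 = 40 users across the intervention practices, before telephone non-response. Because practices continue until those users have completed Assess, chart Yes may predominate, leaving specificity and kappa poorly estimated.

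All of this limits the size of the point. It does not supply the missing Anticipate and Assess items, separate Advise from Assist, or define the pairs.

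**Conclusion.** The point holds in limited form. As written, Aim 3 can address product discussion, a blended quit discussion and parent or household use. It cannot address Anticipate or Assess, has no item for referral or resources, and cannot separate Advise from Assist. Arrange is out of reach because neither instrument records it. Five of 12 survey items have no chart counterpart, which matters only if the analysis sentence is read literally.

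This rests on the printed appendices being the instruments used, on counting Q4 as four items, and on accepting talk about a product (Q4) as a match for being asked about it (chart item 1). It does not affect the primary outcome data. It is a worthwhile, inexpensive correction to what Aim 3 can conclude.

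**What to change.** 1. Add short Yes/No/Don't know items to Appendix F, worded to match Appendix E: asked about future use (item 4), asked about readiness to quit (item 6, users), referral made (item 7), told of resources on hazards (item 8), and told of resources for quitting (item 9). Keep the last two separate, as the chart form does.
2. Split Q6 into being advised not to use or to quit (matching item 5, asked of all youth) and discussing how to quit.
3. Either add an Arrange item to both appendices or state that Aim 3 excludes Arrange.
4. In Section 6.2.5, replace the reference to each survey outcome with a list of matched item pairs, correct the appendix letter, and report Q1, Q2, Q3, Q5 and Q7 descriptively.

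If no items are added, narrow Aim 3 to congruence on discussion of products, quitting and household use; that needs only a change of wording.

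The cost is a questionnaire amendment, a few sentences in the analysis plan, and about one extra minute (an estimate, not a figure in the documents) on a call put at 10 minutes in Section 6.2.3. Estimates for the user-only items, from about 40 users at the stated goal, will be imprecise and should be reported with intervals.
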